## **Secondary objective and outcomes**

1. Categorization of hospitalization status [ Time Frame: 14 days]

The patient will be categorized into one of the following 8 categories depending on status of their hospitalization:

- a. Dead (yes/no)
- b. Hospitalized and receiving mechanical ventilation or Extra Corporal Membrane Oxygenation (ECMO) (yes/no)
- c. Hospitalized and receiving Non-invasive ventilation or "high-flow oxygen device" (yes/no)
- d. Hospitalized and given oxygen supplements different from (2) and (3) (yes/no)
- e. Hospitalized and without oxygen treatment, but receiving other treatment (both related to COVID-19 or other) (yes/no)
- f. Hospitalized for observation (yes/no)
- g. Discharged from hospital with restriction of activity level (yes/no)
- h. Discharged from hospital without any restrictions of activity level (yes/no)

For this analysis, the patient will be assigned a number between 1 and 8. Frequencies for the categories will be presented. Furthermore, the location on the scale for each group will be presented by median (IQR). Significance for differences will be calculated by a Wilcoxon-Sign-rank test (WSR).

Only one category can be "yes".

2. Admitted to intensive care unit, if admitted to ICU then length of stay [ Time Frame: 14 days]

Number of patients admitted to intensive care will be compared using chi-square test. Length of stay in ICU will be analyzed using a t-test. Days not alive within the time frame will be added to days at ICU. If days not alive are equal in the two treatment groups, we will further present days at ICU excluding days not alive.

3. Have used Non-invasive ventilation (NIV) during hospitalization [ Time Frame: 14 days]

Use of NIV will be compared by a chi-square test.

4. Mortality [Time Frame: 30 days ]

Differences in mortality will be displayed using the Kaplan-Meier plots method in combination with the log-rank test and as an adjusted analysis using Cox proportional hazards models, while adjusting for the following variables: Age (per year increase), sex (M/F), COPD GOLD C/D (Yes vs. No), Heart failure NYHA III-IV (Yes vs. no), Active smoker (Yes vs. No).

5. Length of hospitalization [ Time Frame: 14 days]

Length of hospitalization will be compared using t-test.

6. Days alive and discharged from hospital [ Time Frame: 30 days]

This is equal to the primary endpoint but with a longer time frame and will be analyzed like the that.

7. Mortality [ Time Frame: 90 days] – reported in secondary publication.

Differences in mortality will be displayed using the Kaplan-Meier plots method in combination with the log-rank test and as an adjusted analysis using Cox proportional hazards models, while adjusting for the following variables: Age (per year increase), sex (M/F), COPD GOLD C/D (Yes vs. No), Heart failure NYHA III-IV (Yes vs. no), Active smoker (Yes vs. No).

8. Mortality [ Time Frame: 365 days] – reported in secondary publication.

Differences in mortality will be displayed using the Kaplan-Meier plots method in combination with the log-rank test and as an adjusted analysis using Cox proportional hazards models, while adjusting for the following variables: Age (per year increase), sex (M/F), COPD GOLD C/D (Yes vs. No), Heart failure NYHA III-IV (Yes vs. no), Active smoker (Yes vs. No).

9. Number of readmissions (all causes) [ Time Frame: 30 days]

Number of readmission and compared using a Mann-Whitney test, treating death as a competing risk.

10. Number of days using non-invasive ventilation (NIV) [ Time Frame: 14 days]

Number of days using non-invasive ventilation will be compared using t-test, treating death as a competing risk.

11. Change in patient's oxygen partial pressure [ Time Frame: 4 days ]

Delta PaO2 measured in arterial puncture

Changes will be calculated by an ANCOVA method adjusting for baseline values.

12. Change in patient's carbondioxid partial pressure [ Time Frame: 4 days ]

Delta PaCO2 measured in arterial puncture

Changes will be calculated by an ANCOVA method adjusting for baseline values.

13. Level of pH in blood [ Time Frame: 4 days ]

pH measured in arterial puncture

Levels in pH will be compared using t-test

14. Time to no oxygen supplement (or regular oxygen supplement "LTOT") [ Time Frame: 14 days]

Time to no oxygen supplement will be presented by the Kaplan-Meier method and differences calculated by log-rank test.

For all analyses using parametric statistic (t-test, ANCOVA) the distribution will be inspected. Biochemical markers will be transformed if necessary whereas length of stays will not be transformed. If parametric statistics is considered inappropriate a non-parametric alternative will be used. For analyses with a dichotomous outcome Fisher's exact test will be used if the chi-square test is not considered appropriate.

Arrhythmias:

- ECG: Qtc: n (%) patients in both arms who at any time point after baseline had a QTc (F) >500 ms
- N (%) ventricular arrhythmias (apart from ventricular extrasystoles and non-sustained VT).

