#### Secondary endpoints:

## Proactive Prophylaxis With Azithromycin and Chloroquine in Hospitalised Patients With COVID-19 (ProPAC-COVID)

Secondary endpoint no. 1:

Ordinate outcome. The patient is categorized into one of the following 8 categories on day 15:

1. Dead
2. Hospitalised and mechanical ventilation or ExtraCorporalMembraneOxygenation (ECMO)
3. Hospitalised and Non-invasive ventilation or high-flow oxygen device
4. Hospitalised and given oxygen supplements that do not live up to oxygen supplements in (2) or (3) - e.g. oxygen on nasal catheter
5. Hospitalised and do not receive oxygen supplementation but need treatment (COVID-19 related or other)
6. Hospitalised and do not receive oxygen supplements and do not need treatment (just observed)
7. Discharged with restriction on activities, may be free of oxygen depletion or use LTOT ("home oxygen")
8. Discharged, no restrictions on activities

Other secondary endpoints:

- Admitted to the intensive care unit in the two groups (0 vs. 1) during the index admission
  - o For patients admitted to intensive care unit: number of days on intensive care (Length of stay, ICU)
- Have been on Non-Invasive Ventilation (NIV) (0 vs. 1) during index hospitalisation
- Dead at day 30
- Duration (days) of index hospital admission
- Days alive and discharged from hospital within 30 days (summarises both whether the patient is alive and discharged from hospital)
- Dead at day 90 (reported later)
- Dead within 12 months (reported later)
- Number of readmissions for all causes within 30 days
- Number of days on NIV or mechanical ventilation during index admission
- Delta PaO2 day 1 (baseline) to day 4 (72 hours). At the same time oxygen supplements and oxygen systems are registered
- Delta PaCO2 day 1 (baseline) to day 4 (72 hours)
- pH day 4 (72 hours)

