### 3.3.6. Sample size:

#### Randomised controlled study

Prerequisite: Type 1 error rate = 5%. Power = 80%. Two-sided statistics. Group sequential design with one scheduled interim analysis after randomisation of 113 patients (50% recruitment).

Analysis: T-test.

Sample size is calculated based on the following estimates and indicative figures:

Expected duration of hospitalisation with COVID-19: 10 days

SD for "Days alive and discharged within 14 days" in patients with lung disease and COVID-19: 4 days (up to 10 days hospitalization)

Estimated time for improvement/deterioration: 1.5 days.

This requires 226 patients randomised 1:1 with 113 in each group. This is a fixed sample size. It is assumed that most patients complete the intervention.

However, for interim analysis, the Data and Safety Monitoring Board (DSMB) may recommend the steering committee to expand sample size.

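### The ICU length-of-stay t-test covers only patients who reach the ICU, so a drug that lowers total ICU days can show a longer mean stay

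*SAP*

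**What the plan says.** SAP Secondary objective and outcomes, item 2, has two parts. The number of patients admitted to the ICU is compared by chi-square test. Length of stay, which the item's heading makes conditional on having been admitted, is compared by t-test over a 14-day frame.

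Protocol section 3.3.5 sets the same restriction: "For patients admitted to intensive care unit: number of days on intensive care (Length of stay, ICU". It counts stay during the index admission and gives no 14-day limit.

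The SAP adds two rules about death. The first is "Days not alive within the time frame will be added to days at ICU". The second is that a version without days dead will also be shown under a condition: "If days not alive are equal in the two treatment groups".

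Neither document gives patients who never reach the ICU a value, such as zero days, and neither describes an all-randomised version. The SAP's Analysis population section otherwise commits to analysing every randomised patient in the allocated group.

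**The concern.** The trial's hypothesis is that treatment leads to fewer ICU admissions. If it does, the ICU patients in the two arms are no longer comparable: the active arm has lost the patients whose admission was prevented, while their counterparts in the control arm remain. Randomisation does not protect a t-test between these groups. If the prevented admissions are mostly short, the remaining active-arm patients have a longer average stay even though the arm as a whole uses fewer ICU days. A secondary endpoint could then point against a drug that reduces ICU burden.

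The death rules do not repair this. Adding days dead lengthens the values of severe patients, which can widen the gap between those still admitted and those spared. It does nothing for patients never admitted. The condition for the death-free version depends on the observed data, and the SAP does not say what counts as equal.

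**Working it through.** **The plan's own figure.** The only sample-size figure concerns the primary outcome; none is given for ICU stay. Inputs, from protocol section 3.3.6: "Prerequisite: Type 1 error rate = 5%. Power = 80%. Two-sided statistics"; SD, "in patients with lung disease and COVID-19: 4 days (up to 10 days hospitalization"; "Estimated time for improvement/deterioration: 1.5 days".

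n per arm = 2 × 4² × (1.960 + 0.842)² / 1.5² = 111.6, so 112 per arm and 224 in total. The exact t-test calculation gives 112.6, so 113 per arm, which matches "This requires 226 patients randomised 1:1 with 113 in each group". The figure reproduces, and the ICU point does not touch it. It supplies the 113 per arm used below.

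**Assumptions.** The documents give no ICU rate, stay length or severity mix. Two models follow; every ICU input in them is assumed.

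**Model A: log-normal stays, median 8 days, sigma 0.6, cut at the 14-day frame.** The shortest third of stays lies below 8 × exp(0.6 × −0.431) = 6.2 days. Treatment is assumed to prevent exactly these admissions.

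- 14-day cap: mean among ICU patients 8.5 (control) and 10.6 (active). Ratio of total days = (2/3) × 10.57 / 8.49 = 0.83, a fall of 17%.
- 10-day cap (ICU entry some days after recruitment): 7.5 and 9.0. Ratio = (2/3) × 9.04 / 7.47 = 0.81, a fall of 19%.

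**Model B: two kinds of ICU patient.** Control ICU rate 20%, half mild (mean 4 days) and half severe (mean 11 days, days dead included). Treatment prevents a fraction f of the mild admissions.

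- ICU-only mean, active = [0.10(1 − f) × 4 + 0.10 × 11] / [0.10(1 − f) + 0.10]. Control: 1.50 / 0.20 = 7.50.
- All-randomised mean, active = 0.10(1 − f) × 4 + 0.10 × 11, with zero days if never admitted. Control: 1.50.

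At f = 0.5: ICU-only 1.30 / 0.15 = 8.67, a difference of +1.17; all randomised 1.30, a difference of −0.20.

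| f | ICU-only difference (days) | All-randomised difference (days) | Trials with ICU-only difference against the drug | Of all trials, against the drug at p < 0.05 |
|---|---|---|---|---|
| 0.25 | +0.50 | −0.10 | 63% | 5% |
| 0.50 | +1.17 | −0.20 | 80% | 11% |
| 0.75 | +2.10 | −0.30 | 93% | 28% |
| 1.00 | +3.50 | −0.40 | over 99% | 64% |

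The last two columns come from 3,000 simulated trials per row at 113 per arm (SD 3 days within each kind, stays rounded and held to 1–14 days). At f = 0.5 about 23 control and 17 active patients enter the t-test.

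**Sensitivity, with half of the stated admissions prevented.**

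- ICU rate 10% or 30%: the ICU-only difference stays at +1.17; all-randomised −0.10 or −0.30.
- Mild/severe means 6/9 or 3/12: ICU-only +0.50 or +1.50.
- Mild and severe prevented equally: ICU-only 0; all-randomised −0.75.
- Equal stays of 7 days in both kinds: ICU-only 0; all-randomised −0.35.
- Only severe prevented: ICU-only −1.17; all-randomised −0.55.

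**Companion test.** For a 25% relative reduction in ICU admission at 113 per arm, power is about 10%, 17% and 25% at control rates of 10%, 20% and 30%.

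**The case against.** The strongest reply is that the stay is not reported alone. The same item first compares ICU admission by chi-square, which is valid in all randomised patients. The primary outcome, the eight-category status and 30-day mortality are also all-patient comparisons. A reader who sees fewer admissions beside a longer mean stay may understand why. This stands as mitigation. But the chi-square does not measure ICU days, and its power is low enough that it may not visibly offset a misleading stay result.

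The SAP also allows a non-parametric alternative where parametric methods are unsuitable. That changes the test, not the patients in it.

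Several stronger readings are tempting, and the documents do not support them:

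- **That an effective drug would look harmful.** The sign depends on which admissions are prevented. It can be zero or favourable, and a significant wrong-way result is uncommon unless most mild admissions are prevented. Model A removes exactly the shortest stays, the most adverse pattern for that fraction.
- **That mean stay would rise from 9.6 to 12.2 days.** Model A gives this without a cap, but the SAP's frame is 14 days and about 17% of those stays exceed it.
- **That patients who die on the ward are left out.** The heading suggests it, but the SAP does not say whether the added days cover all deaths or only those of ICU patients. The scoring is unspecified.
- **That the equality condition will almost never be met.** This assumes exact numerical equality, which the SAP does not state. The defect is that the condition is undefined and depends on the data.

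**Conclusion.** The concern holds as a conditional statement. The planned t-test compares groups formed by a post-randomisation event that treatment may change, so its result is not an intention-to-treat effect. Whenever the prevented admissions have shorter stays than the rest, mean stay among ICU patients rises while total ICU days fall.

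Under the assumed inputs the distortion is about two days in Model A with a 14-day cap, and +0.5 to +3.5 days in Model B against −0.1 to −0.4 day over all randomised patients. Confidence is high about the selection and low about sign and size, because the documents supply no ICU figures. This is one part of one secondary item; the primary outcome and the 226 patients are unaffected. It should be corrected, but it does not threaten the trial's main conclusion.

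**What to change.** Before the allocation is revealed, change SAP item 2 and the matching endpoint in protocol section 3.3.5:

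- Make the tested outcome days alive and out of ICU to day 14 in all randomised patients. A patient never admitted has zero ICU days, and every day dead counts as lost wherever the death occurs.
- Test it by t-test with a rank-test sensitivity analysis, as for the primary outcome.
- Delete the clause about equal days not alive; every death is then scored and it is not needed.
- Keep the chi-square on ICU admission, and report stay among ICU patients as description only.
- Reconcile the window: 14 days in the SAP, index admission in the protocol.

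The cost is wording. The data are the same and the sample size does not change. However, this alters a protocol endpoint as well as the SAP. The all-patient difference will also be small in days, because most patients contribute no ICU time. In Model B, if nobody dies outside the ICU group, days alive and out of ICU is 14 minus the all-randomised mean, so at f = 0.5 it is 12.50 in control and 12.70 in active, a difference of 0.20 day.

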#### Exclusion criteria:

- At the time of recruitment, the patient uses  $>5$  LO2/min (equivalent to 40% FiO2 if measured)
- Known intolerance/allergy to azithromycin or hydroxychloroquine or hypersensitivity to quinine or 4-aminoquinoline derivatives

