## **DATA ANALYSIS**

### **Descriptive analyses – Baseline characteristics at study enrollment (defined as day 1).**

The following baseline characteristics of the study population will be summarized separately within each randomized group:

- Age, median (IQR), y
- Male sex, n (%)
- Ethnicity (Caucasian, African (incl. Afro-American), Asian, Inuit, Unknown/other)
- Body mass index ( $\text{kg}/\text{m}^2$ , median, IQR)
- Current smoker, n (%)
- Ex-smoker, n (%)
- Nonsmoker, n (%)
- Pack-years history (median, IQR, y)
- Use of oxygen therapy, n (%)
- Use of CPAP, n (%)
- Use of noninvasive mechanical ventilation, n (%)
- Infiltrate on Chest X-ray, n (%)
- Oxygen consumption: L/min (median, IQR)
- Oxygen consumption:  $\text{FiO}_2$  (median, IQR)

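### NIV at entry is allowed, but the NIV endpoint counts any use in the admission, so patients already on NIV at randomisation score as events whatever the treatment does

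*SAP*

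**What the plan says.** **Eligibility.** Protocol 3.3 admits patients who have been in hospital for up to 48 hours, from emergency, respiratory or internal medicine departments. The only exclusion that concerns respiratory support begins "At the time of recruitment, the patient uses" and sets a limit of 5 L/min of oxygen (given as equivalent to 40% FiO2). NIV, CPAP and earlier ICU care are not on the exclusion list.

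**Baseline.** Among the characteristics to be tabulated at enrolment (day 1), the SAP lists "Use of noninvasive mechanical ventilation, n" (%). CPAP is listed as well.

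**Endpoints in the protocol (3.3.5).** "Have been on Non-Invasive Ventilation (NIV) (0 vs. 1) during index hospitalisation" and "Admitted to the intensive care unit in the two groups (0 vs. 1) during the index admission".

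**Endpoints in the SAP (Secondary objective and outcomes).** Item 3 is "Have used Non-invasive ventilation (NIV) during hospitalization [ Time Frame: 14 days"], compared by chi-square. Item 2, ICU admission, has the same 14-day frame but does not refer to the hospitalisation. Neither item says when the 14 days begin, and neither has a rule for a patient who is on NIV at entry.

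**The concern.** Reducing the risk of NIV and of intensive care is a stated aim (Protocol 1.2). NIV that is already running at randomisation cannot be prevented by a treatment that starts afterwards. If such patients are scored as events, each arm receives a block of events that carries no information about treatment. This pulls the risk ratio towards 1 and costs power. Allocation is stratified by age, site and chronic lung disease but not by NIV, so an uneven split of baseline users adds noise to the comparison.

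The two documents also define different windows. The protocol uses the whole index admission, which can begin up to 48 hours before randomisation and can run past day 14. The SAP uses 14 days from a point it does not name.

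**Working it through.** **1. Which events are counted under each wording**

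| Patient | Protocol 3.3.5 | SAP, if 14 days start at recruitment | SAP, if 14 days start at admission |
|---|---|---|---|
| On NIV at randomisation and continues | counted | counted | counted |
| NIV ended before randomisation | counted | not counted | counted |
| ICU stay ended before randomisation | counted | not counted | counted |
| NIV or ICU care first begun after randomisation, within the SAP window | counted | counted | counted |

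The first row does not depend on the reading, and it is the core of the point. The second and third rows depend on the missing start date.

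**2. The plan's own sample size**

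Inputs from Protocol 3.3.6: "Prerequisite: Type 1 error rate = 5%. Power = 80%. Two-sided statistics"; "Estimated time for improvement/deterioration: 1.5 days"; SD "in patients with lung disease and COVID-19: 4 days".

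Normal approximation: n per arm = 2 × [4 × (1.960 + 0.842) / 1.5]² = 111.6, so 112 per arm and 224 in total. The exact two-sample t-test gives 112.6, so 113 per arm and 226 in total, with power 80.1%. The stated 226 is reproduced. It was set for the primary outcome and is not affected here.

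**3. Illustration for the NIV endpoint**

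The documents give no NIV rate and no share on NIV at entry. Assumptions:
- new NIV is 20% in control and 10% on treatment among patients free of NIV at entry;
- a share b of each arm is on NIV at entry and scores 1;
- 113 per arm, two-sided 5%.

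Observed rate in an arm = b + (1 − b) × new-NIV rate.

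Power = Φ[(d − 1.96 × SE0) / SE1], where d is the difference in rates, SE0 the pooled and SE1 the unpooled standard error. For the comparison restricted to new NIV, n per arm = 113 × (1 − b) and the rates stay at 20% and 10%.

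Worked line for b = 5%:
- control 0.05 + 0.95 × 0.20 = 0.240; treated 0.05 + 0.95 × 0.10 = 0.145; d = 0.095; risk ratio 0.60;
- pooled rate 0.1925; SE0 = √(2 × 0.1925 × 0.8075 / 113) = 0.0525; SE1 = √[(0.240 × 0.760 + 0.145 × 0.855) / 113] = 0.0521;
- power = Φ(−0.15) = 44.0%;
- restricted: n = 113 × 0.95 = 107.35 per arm, power 53.7%.

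| Share on NIV at entry | Rates as written | Risk ratio as written | Power as written | Power, new NIV only (risk ratio 0.50) |
|---|---|---|---|---|
| 0% | 20.0% vs 10.0% | 0.50 | 55.8% | 55.8% |
| 2% | 21.6% vs 11.8% | 0.55 | 50.6% | 55.0% |
| 5% | 24.0% vs 14.5% | 0.60 | 44.0% | 53.7% |
| 10% | 28.0% vs 19.0% | 0.68 | 35.7% | 51.5% |
| 15% | 32.0% vs 23.5% | 0.73 | 29.6% | 49.2% |

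Other assumed rates at b = 5%: with new NIV 10% vs 5%, power is 19.3% as written against 28.4% for new NIV only. With 30% vs 15% it is 68.3% against 75.3%.

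**4. Chance imbalance**

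Under simple random allocation of 113 of 226 (hypergeometric), the chance that the arms differ by 5 or more baseline NIV users is 21.5% if there are 11 such users and 6.0% if there are 5.

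No calculation is offered for ICU, because the documents give neither a rate nor a baseline ICU field.

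**The case against.** The strongest reply is that the SAP does limit the window. The only 14-day period whose start the SAP states is that of the primary outcome, which runs from recruitment, and enrolment is defined as day 1. If items 2 and 3 share that start, NIV or ICU care that was over before randomisation is not counted. This is a natural reading and it stands. A reader might infer that the plan definitely scores pre-randomisation events as outcomes. The protocol's wording does, but the SAP leaves it open. The reply does not help with NIV that is running at randomisation and continues, which counts on either reading.

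The ICU side is weaker than the NIV side, and this also stands. The ICU is not a listed place of recruitment, and SAP item 2 does not speak of the hospitalisation. A pre-randomisation ICU event needs a stay that began and ended within the first 48 hours, in a patient then on no more than 5 L/min. That is probably rare.

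A reader might also take the baseline table as proof that the sponsor expects patients on NIV. It shows only that NIV will be tabulated. The oxygen limit probably keeps the number small, and at 2% the loss of power is modest.

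Finally, a reader might call this a bias between arms. It is not a systematic one. Baseline NIV falls on both arms by chance, and stratification by chronic lung disease may even out some of it. What remains is dilution and noise.

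Restricting the analysis also departs from the SAP's rule of analysing all randomised patients. That is a fair objection, and the fix below allows for it.

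**Conclusion.** The point holds for NIV. Eligibility allows NIV at entry, the endpoint is ever/never over the admission, the test is unadjusted, and nothing separates new from continuing NIV. For care that ended before randomisation, the protocol counts it, and the SAP does so only if its 14 days start before randomisation. For ICU this is a gap in wording with probably little effect.

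The consequence is confined to secondary endpoints. It is a risk ratio pulled towards 1, lower power and some chance noise. The size is unknown. With new NIV of 20% vs 10%, the power lost relative to counting new NIV only is about 4 percentage points at 2% on NIV at entry, 10 at 5% and 16 at 10%. All of these rates are assumptions. Even with nobody on NIV at entry, power for this endpoint would be only 56% under them. The primary outcome and the 226 patients are untouched.

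The plan already handles the same issue elsewhere: the primary outcome is counted from recruitment, the QTc outcome is limited to the time after baseline, and the blood-gas changes are adjusted for baseline. NIV and ICU should be brought into line.

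**What to change.** 1. In Protocol 3.3.5 and SAP items 2 and 3, define the events as NIV started, or ICU admission occurring, from randomisation to day 14. This states the start of the window and reconciles the protocol's index admission with the SAP's 14 days.
2. Make the main NIV comparison among patients not on NIV at baseline, using the field already planned for the baseline table. The restriction uses a pre-randomisation characteristic, so it keeps the randomised comparison.
3. Report baseline NIV users separately by arm, and keep the all-randomised comparison as a supplementary analysis.
4. Apply the same start date to ICU length of stay (item 2) and to days on NIV (item 10).

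Eligibility need not and should not change for this purpose.

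The cost is wording in both documents, with no new data and no change in sample size. The downside is that the few patients on NIV at baseline leave the main NIV comparison, which is then not on the full intention-to-treat set. The supplementary analysis covers that.

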## Proactive Prophylaxis With Azithromycin and Chloroquine in Hospitalised Patients With COVID-19 (ProPAC-COVID)

Follow-up is done on days 14, 29, 90 and 365 days, by accessing the electronic medical record system. The specific information obtained, and its purpose can be found in section 3.3.3.

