### Regarding dosage

The Summary of Product Characteristics for Azithromycin suggests 500mg/day for three days or 500mg/day for one day and then 250mg daily for four days. However, other clinical studies have found a positive effect of a daily dose of 250 mg for prolonged periods as prophylactic treatment. Mortality among hospitalised patients with COVID-19 is quite high and the median time for hospitalisation is 10-15 days, so it seems reasonable to give patients prophylactic dose for 12 days.

The dosing of hydroxychloroquine follows the summary of product characteristics.

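### SAP items 2, 3, 5 and 10 cut the ICU, ventilation and length-of-stay endpoints at 14 days, where the protocol counts them over the whole index admission

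*SAP*

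**What the plan says.** The endpoints side by side (protocol section 3.3.5, Secondary endpoints; SAP, Secondary objective and outcomes):

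| Endpoint | Protocol | SAP |
|---|---|---|
| ICU | "Admitted to the intensive care unit in the two groups (0 vs. 1) during the index admission", with ICU days listed beneath it for those admitted | Item 2: "Admitted to intensive care unit, if admitted to ICU then length of stay [ Time Frame: 14 days" |
| NIV use | "Have been on Non-Invasive Ventilation (NIV) (0 vs. 1) during index hospitalisation" | Item 3: use in hospital, 14-day frame |
| Length of stay | "Duration (days) of index hospital admission" | Item 5: "Length of hospitalization [ Time Frame: 14 days", compared by t-test |
| Ventilation days | "Number of days on NIV or mechanical ventilation during index admission" | Item 10: NIV days only, 14-day frame |

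The SAP section on blinding of the statistician says that the plan agrees strictly with the approved protocol. No section explains the change of window. Item 5 does not say how a stay beyond day 14 or a death in hospital enters the t-test.

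On expected stay, protocol section 3.3.6 plans for 10 days, and the dosage text in 3.3.4 says that "the median time for hospitalisation is 10-15 days". On data, the protocol says: "Follow-up is done on days 14, 29, 90 and 365 days, by accessing the electronic medical record system".

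**The concern.** Shorter hospitalisation and fewer ICU admissions are the trial's stated hypothesis, so these secondary endpoints speak to it directly. Day 14 falls inside or close to the stay that the documents expect. Under the SAP, a 15-day and a 35-day stay both score 14. A patient first moved to the ICU, or first given NIV, on day 16 of the same admission counts as never having had the event. The reported estimates would then describe the first 14 days, while a reader of the protocol would take them to describe the whole admission.

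The 14-day window is also that of the primary outcome, the count of days alive and outside hospital in the 14 days after recruitment (DAOH14). Item 5 may therefore add little to it.

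**Working it through.** **1. The plan's own sample size.** Inputs from protocol 3.3.6: difference 1.5 days, SD 4, two-sided 5%, power 80%. The normal formula gives 2 × (1.960 + 0.842)² × 16 / 2.25 = 111.6 per arm. With the exact t-test, 112 per arm gives 79.8% power and 113 gives 80.1%. So 113 per arm, 226 in all, reproduces. This point does not dispute it.

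**2. Does the bracket set the window?** The SAP's frames differ by item (4, 14, 30, 90 and 365 days). Item 6 is described as the primary endpoint over a longer frame. Item 2 adds days not alive inside the frame to ICU days. The frame therefore enters the calculation. Item 3 is also ambiguous, because it refers both to the hospitalisation and to 14 days.

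**3. Share still in hospital after day 14.** The documents give no distribution, so I assume a log-normal stay with median M and log-SD s: P(stay > 14) = 1 − Φ(ln(14/M)/s).

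| Median M (days) | s = 0.5 | s = 0.7 | s = 0.9 |
|---|---|---|---|
| 5 | 2% | 7% | 13% |
| 10 | 25% | 32% | 35% |
| 12.5 | 41% | 44% | 45% |
| 15 | 55% | 54% | 53% |

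An exponential stay gives 25% for a mean of 10 days, 38% for a median of 10 and 52% for a median of 15.

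These figures count stay from recruitment. Suppose instead that the quoted stays run from admission and every patient is enrolled at the 48-hour limit. The threshold is then 16 days, and the shares are 17-30% at a median of 10 and 45-47% at 15.

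**4. What the cap does to a difference in stay.** Assume s = 0.7, a 15% shorter stay in every patient and 113 per arm. The uncapped mean difference is 0.15 × M × exp(0.7²/2). The standardised difference is the mean difference over the pooled SD.

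| Median, cap | Difference (days) | Pooled SD | Standardised | Power |
|---|---|---|---|---|
| 10, none | 1.92 | 9.43 | 0.20 | 33% |
| 10, day 14 | 0.88 | 3.99 | 0.22 | 38% |
| 10, day 30 | 1.60 | 7.31 | 0.22 | 38% |
| 15, none | 2.87 | 14.14 | 0.20 | 33% |
| 15, day 14 | 0.71 | 3.46 | 0.20 | 34% |
| 15, day 30 | 1.89 | 8.45 | 0.22 | 39% |

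The cap shrinks the difference and the SD together. The quantity estimated changes; the power hardly does.

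**5. Overlap with the primary outcome.** For a patient alive at day 14 and not readmitted, with stay counted from recruitment, min(stay, 14) = 14 − DAOH14. In that group the t-test for item 5 gives the same p-value as the primary test. Outside it the two measures separate, because an early death shortens the stay but also holds DAOH14 low. Simulated correlations with DAOH14 follow, for medians of 10 to 15 days, log-SD 0.6 and 0.9, readmission 0 or 10%, and death at the end of the stay independent of its length:

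| In-hospital deaths | Stay capped at 14 days | Full index stay |
|---|---|---|
| 0% | −0.99 to −1.00 | −0.49 to −0.78 |
| 5% | −0.93 to −0.96 | −0.47 to −0.74 |
| 25% (protocol 2.1) | −0.75 to −0.82 | −0.40 to −0.58 |

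**The case against.** The best defence is that little is lost. The trial plans for a 10-day stay and the SAP expects DAOH14 of at least 4. Both point to the lower end of the range, and patients on more than 5 L/min of oxygen at recruitment are excluded. Item 6 follows hospital days to day 30 and item 4 follows mortality to day 30. ICU and NIV starts may cluster early. All of this bears on the size of the loss and makes the 53-55% figure the far end. It does not remove the mismatch, and neither item 6 nor item 4 counts a late ICU or NIV event.

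Four stronger readings are tempting, and the documents do not support them:

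- **The cap hides a treatment effect.** A reader might infer this from the fall in raw days (1.92 to 0.88). The SD falls too, and power stays about the same.
- **The ICU result will mislead because the drug may only delay admission past day 14.** This is possible, but the documents give no timing for ICU or NIV events. The share still in hospital is not the share with late events.
- **Item 5 simply repeats the primary test.** That needs survival, no readmission and counting from recruitment. Item 5 does not name its starting point. If DAOH14 falls below 4, the SAP presents the 21-day count instead, and the identity no longer ties item 5 to the outcome presented.
- **An ICU transfer on the last dosing day, day 15, falls outside the window.** The SAP calls enrolment day 1, so 14 days after recruitment can be read as day 15. The example depends on that convention.

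**Conclusion.** The concern holds as a mismatch between protocol and SAP in four secondary endpoints, two of them tied directly to the hypothesis. If the SAP is followed, hospital days and ICU or NIV events after day 14 are dropped for about 25-35% of patients at a median stay of 10 days, rising to 53-55% at 15 and falling to 2-13% at 5. These shares rest on an assumed log-normal stay counted from recruitment. The consequence is a different and smaller estimand under the same endpoint name, not a material loss of power. The loss of late ICU and NIV events cannot be sized from the documents. Overlap between item 5 and the primary outcome is near complete at low mortality and clearly weaker near 25%. The primary outcome and the sample size are unaffected. The SAP should be corrected before unblinding.

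**What to change.** - In SAP items 2, 3, 5 and 10, replace the 14-day frame with the index admission, as in protocol 3.3.5. Restore mechanical ventilation in item 10.
- If a practical cut-off such as day 30 is preferred, declare it as a cap that departs from the protocol, with a reason. On the same log-normal assumption, 1-11% of patients would still be in hospital after day 30 at a median of 10 days, and 8-22% at 15.
- State whether stay counts from admission or recruitment, and how deaths and patients still admitted at the cut-off are scored. Item 2 needs particular care: its addition of days not alive has no end point once the frame is the index admission.
- Keep the 14-day versions as supportive analyses.

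The cost is SAP wording and later availability of these results. Medical records are already due for review at days 29, 90 and 365, and items 4, 6 and 9 already need 30-day data. If the sponsor wishes to keep 14 days, the change should be declared and justified before unblinding.
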